## 5.8. Efficacy and Safety Analyses

No formal hypothesis testing is planned. All efficacy analyses will be performed using the ITT population.

In general, the below rules apply to the derivations of efficacy endpoints related to hemoglobin and RBC transfusion data unless specified otherwise:

- Hemoglobin measurements within 7 days following RBC transfusion will be excluded from the efficacy analysis
- For each patient, all efficacy endpoints will be derived based on an analysis cutoff day, defined as the last dose + 56 days or the last date from transfusion record data, whichever is earlier.

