### 5.8.2. Secondary Efficacy Endpoints

#### 5.8.2.1. Erythroid Response (modified HI-E from IWG 2006 criteria)

Erythroid response (modified HI-E from IWG 2006 criteria) is defined as the proportion of patients with:

- A mean hemoglobin (Hgb) increase  $\geq 1.5$  g/dL over an 8-week period as compared to baseline, not influenced by RBC transfusion, in LTB patients.
- A decrease of  $\geq 4$  units or  $\geq 50\%$  of units of RBCs transfused over a period of 8 weeks, relative to the 8 weeks immediately prior to Day 1, in HTB patients.

A point estimate of the proportion of patients achieving a modified erythroid response will be presented along with its associated exact 95% confidence interval based on binomial distribution.

The complete hemoglobin measurements and RBC transfusion records will be listed for each patient.

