#### 5.8.2.3. HI-E Response Rate

Erythroid (HI-E) response will be defined following IWG 2006 criteria.

- For low transfusion burden (LTB) patients, a hemoglobin increase of  $\geq 1.5$  g/dL from baseline during any rolling 8-week period in the absence of transfusion. The rolling 8-week period starts and ends at a hemoglobin measurement date with duration  $\geq 8$  weeks.

- For high transfusion burden (HTB) patients, a reduction by  $\geq 4$  RBC units transfused during any rolling 8-week interval on treatment compared to baseline.

A point estimate of the proportion of HI-E responders will be presented along with its associated exact 95% confidence interval based on binomial distribution. HI-E response will also be listed for each patient.

There are two versions of a HI-E response for LTB patients.

- All hemoglobin values increase of  $\geq 1.5$  g/dL from baseline during any rolling 8-week period in the absence of transfusion.
- Mean hemoglobin value increase of  $\geq 1.5$  g/dL from baseline during any rolling 8-week period in the absence of transfusion.

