#### **5.8.2.5. Time to and Duration of HI-E Response**

Time to and duration of HI-E response will be analyzed for HI-E responders only.

Time to HI-E response will be defined as the time from the first dose date to the first date of any rolling 8-week interval achieving HI-E response.

Duration of HI-E response will be defined as below for LTB and HTB patients, respectively:

- For LTB patients, duration of HI-E response will be calculated as the longest interval during which all hemoglobin measurements have an increase of  $\geq 1.5$  g/dL from baseline.
- For HTB patients, duration of HI-E response will be calculated for the longest such interval as the time from the start date of the first rolling 8-week interval achieving hematologic response to the end date of the last consecutive rolling 8-week interval achieving response.

When there are multiple disjoint intervals with response, the longest interval will be used. Patients with response ongoing by the analysis cutoff day will be censored at that date.

Both time to and duration of HI-E response will be analyzed as continuous variables and summarized by descriptive statistics. In addition, duration of HI-E response will also be analyzed as a time to event endpoint. The survival curves will be estimated using Kaplan-Meier method if the number of patients is more than 5.

HI-E responders may experience multiple periods of  $\geq 8$  weeks of HI-E response. For all HI-E responders, the number of episodes and cumulative duration will be summarized. As an exploratory analysis, the cumulative duration of the multiple responses will be analyzed using Kaplan-Meier method.

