### 5.13. Changes in Conduct or Planned Analyses from the Protocol

Major changes between SAP and the planned analysis in Protocol are described below:

Item	Difference Between Protocol and SAP
NTD/TD	In SAP, the terms LTB/HTB are used in place of NTD/TD in protocol.
mITT	In the SAP, ITT is used in place of mITT in the protocol.
Secondary objectives: time to and duration of mHI-E	The secondary endpoints time to and duration of mHI-E will not be analyzed.
Efficacy Evaluable Population (EE)	Analysis on Efficacy Evaluable population will not be performed. All analyses are on ITT population
Definition of baseline hemoglobin	Protocol definition: Baseline hemoglobin will be the average of at least two measures (not influenced by transfusion within 7 days of measurement); one measure performed within one day prior to Cycle 1 Day 1 and the other performed 7-28 days prior to Cycle 1 Day 1. This definition is revised in this SAP to reflect the derivation rule implemented for this study.

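### The duration-of-HI-E rule for low-transfusion-burden (LTB) patients lets an interval run across a transfusion and does not say which response version selects the patients

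*SAP*

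**What the plan says.** **Response.** SAP 5.8.2.3 states: "There are two versions of a HI-E response for LTB patients". One requires every hemoglobin value, the other the mean value, to be at least 1.5 g/dL above baseline. Both carry the condition "from baseline during any rolling 8-week period in the absence of transfusion", and the window must start and end on a measurement date and last at least 8 weeks.

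**Duration.** SAP 5.8.2.5 opens: "Time to and duration of HI-E response will be analyzed for HI-E responders only". It does not say which version makes a patient a responder. For LTB patients, "duration of HI-E response will be calculated as the longest interval during which all hemoglobin measurements have an increase of" at least 1.5 g/dL from baseline. The sentence has no transfusion condition and no minimum length. The matching rule for high-transfusion-burden (HTB) patients is built from 8-week windows that themselves achieve response, so it inherits the response definition.

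**Handling of transfusions.** The general rule in SAP 5.8 is: "Hemoglobin measurements within 7 days following RBC transfusion will be excluded from the efficacy analysis". Protocol 10.2.2 asks for a hemoglobin value just before every on-study transfusion, in NTD and TD patients alike. The SAP does not say whether those values count in this derivation.

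**Modified response.** SAP 5.8.2.1 defines mHI-E for LTB patients by the mean hemoglobin rise, which is nearly the mean version of 5.8.2.3. SAP 5.13 adds: "The secondary endpoints time to and duration of mHI-E will not be analyzed".

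**The concern.** Response and its duration should rest on the same condition. Here response requires freedom from transfusion and duration does not. LTB patients can be transfused: SAP 5.1 defines them by fewer than 4 units in 8 weeks, not by none. A patient transfused part-way through a run of raised values can be counted as still in response, or censored as ongoing in the Kaplan-Meier summary.

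The unnamed version adds a second problem. A programmer could select patients by the mean test and then measure duration by the all-values test, and some responders would then have less than the 8 weeks that define response. The logistic regressions in SAP 5.8.4 use IWG HI-E response and also name no version. Duration of HI-E is a listed secondary objective, and two careful programmers could report different patients and different durations.

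**Working it through.** The documents give no figure for this point, so there is none to reproduce. I applied the written rules to constructed series and to a small simulation.

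**Inputs from the documents**
- Threshold: +1.5 g/dL (SAP 5.8.2.3, 5.8.2.5).
- Window: at least 8 weeks = 56 days.
- Visit spacing in A536-05: 21 days (protocol Section 2). The shortest qualifying window has four scheduled values and spans 3 × 21 = 63 days. Direct roll-over patients also contribute A536-03 data (SAP 4.1), where values are closer together; that is not modeled.
- Exclusion: 7 days after a transfusion (SAP 5.8).

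**Convention (mine).** An interval runs from its first to its last qualifying value, so a single value gives 0 days.

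**1. All-values responders.** The qualifying window is itself an interval in which every value qualifies. Duration is therefore at least 56 days. Shorter durations can come only from mean-only responders.

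**2. A mean-only responder.** Rises of +2.5, +1.2, +2.4 and +1.3 on days 22, 43, 64 and 85:
- Mean = (2.5 + 1.2 + 2.4 + 1.3) / 4 = 7.4 / 4 = 1.85, over 85 − 22 = 63 days, so the mean version is met.
- Two values are below 1.5, so the all-values version is not met.
- No two consecutive values qualify, so the duration is 0 days.

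**3. A transfused responder.** Rises of +1.8, +1.7, +1.9 and +1.6 on days 22 to 85; transfusion on day 100; +0.9 on day 106; then +1.7, +1.6 and +1.8 on days 127, 148 and 169. Day 106 is 6 days after transfusion, so that low value is excluded.

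| Pre-transfusion value (day 100) | Rule as written | Transfusion ends the interval |
|---|---|---|
| Not in the data | 169 − 22 = 147 days | 85 − 22 = 63 days |
| +0.4, counted | 85 − 22 = 63 days | 63 days |
| +1.6, counted | 169 − 22 = 147 days | 100 − 22 = 78 days |

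The run after the transfusion is 169 − 127 = 42 days and is never the longest. If the interval were closed on the transfusion date and not at the last value, the first row would also read 78 days.

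The third row can arise in practice. Protocol 10.2.2 allows transfusion for symptoms or comorbidity. In addition, any baseline below 9.0 − 1.5 = 7.5 g/dL lets a patient be 1.5 g/dL up and still under the 9 g/dL level named there. With an assumed baseline of 7.0 g/dL, a value of 8.6 is a rise of 1.6.

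**4. Range for mean-only responders.** The documents give no mean or SD for the rise. I assumed independent normal values about a constant mean, SD 0.4 to 1.0 g/dL, four-visit windows, and 600 series per setting. The table shows the share of mean-version responders with an all-values duration under 56 days.

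| Mean rise (g/dL) | 16 visits | 86 visits |
|---|---|---|
| 1.0 | 92–97% | 60–97% |
| 1.5 | 60–63% | 4–5% |
| 2.0 | 0–18% | 0% |
| 2.5 | 0–1% | 0% |

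At a mean rise of 1.5, one window passes the mean test with probability 0.5 and the all-values test with probability 0.5⁴ = 0.0625, whatever the SD. At the 97% end (mean 1.0, SD 0.4), mean-version response is itself uncommon: 5.7% over 16 visits and 31% over 86.

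**The case against.** The strongest reply is that the SAP, read as a whole, already works. If the mean version is mHI-E under another name, SAP 5.13 removes its duration from the analysis. The all-values rule in 5.8.2.5 then matches the all-values version in 5.8.2.3, and no responder falls below 56 days. Section 5.8.2.5 also speaks of intervals with response and of response periods of at least 8 weeks, which can be read as carrying over the transfusion condition. The 7-day exclusion and the pre-transfusion values give further protection, since a low pre-transfusion value ends the interval.

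Much of this stands. A reader might infer that the SAP gives responders durations under 8 weeks as a matter of course. It does not: that needs mean-only responders to enter, and the text leaves this open because 5.8.2.3 calls both versions HI-E. A reader might infer that LTB durations are generally propped up by transfusion. The documents do not show how often the remaining gap occurs. Nor do they support a cutoff other than their own 7 days for when a value is free of transfusion. Finally, a reader might infer that the version is left to be picked once results are known. Both versions are written down, the SAP is signed before database lock, and there is no primary efficacy endpoint or hypothesis test.

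What does not stand is that the 7-day rule closes the transfusion gap. It deletes values without ending the interval, and in case 3 it deletes the very value that would have ended it. SAP 5.8.2.3 adds its own transfusion condition on top of that rule, so the SAP does not treat the exclusion as sufficient for response.

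**Conclusion.** The point holds in two parts of different strength.

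The transfusion part is a fault in the stated rule. As written, an LTB duration can cross a transfusion when the pre-transfusion value is absent from the analysis data or still at least 1.5 g/dL above baseline. The constructed case shows 147 days against 63 or 78; it illustrates the mechanism and does not estimate frequency.

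The under-8-weeks part is an ambiguity. It bites only if mean-only responders enter the duration analysis. The 0% to 97% range rests wholly on assumed means, SDs and independent values, and no narrower figure can be defended from the documents.

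The endpoint is secondary and descriptive and the study has no formal sample size calculation, so no error rate or power is affected. The correction is still worth making, because the same data can yield different durations under the present text.

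**What to change.** 1. Use the all-values version as IWG HI-E in SAP 5.8.2.3, 5.8.2.5 and 5.8.4. Label the mean version mHI-E and align it with 5.8.2.1. SAP 5.13 then applies to it without doubt.
2. Keep the longest-interval rule. Define the LTB interval as at least 8 weeks in the absence of RBC transfusion, ending at the first value below +1.5 g/dL or the first transfusion, whichever comes first.
3. State that pre-transfusion hemoglobin counts, and that a value drawn on the transfusion day before the transfusion is not caught by the 7-day exclusion.
4. State whether the end date is the last qualifying value or the date of the ending event.

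The cost is a few lines of SAP text and minor code changes before database lock. Some LTB durations will be shorter, and the LTB HI-E rate may be lower than under the mean version. The mean-based rate is still reported as mHI-E.

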#### 3.1. Study Design

Patients in all cohorts will receive ACE-536, administered subcutaneously (SC), every 3 weeks for up to 87 cycles or up to 1825 days, whichever occurs first. Dose titration(s), delay(s) and dose reduction(s) may be required for individual patients as outlined in the Individual Dose Modification Rules (protocol Section 10.8).

The base study A536-03 is a phase 2, open-label, ascending dose study to evaluate the effects of ACE-536 on anemia in patients with low or intermediate-1 risk MDS who are not currently receiving treatment with an erythropoiesis-stimulating agent (ESA). A total of up to 153 patients may be enrolled in the base study A536-03 and may be eligible for study A536-05.

Consenting patients that meet the A536-05 eligibility criteria may immediately roll over from A536-03 to study A536-05. These patients will forego the Post-Treatment Follow-up (PTFU) and End of Study (EOS) visits of A536-03 to begin study A536-05. For these patients, C1D1 of A536-05 may take place 28 ( $\pm$  7) days after the last dose administered in the base study A536-03, which may coincide with the patient's A536-03 End of Treatment (EOT) visit. These patients will be considered "patients without treatment interruption." Patients enrolled in expansion cohorts 2 and 3 in Study A536-03 must meet the "patients without treatment interruption" criteria to be considered for the A536-05 study, unless otherwise prospectively approved by the sponsor.

Patients who complete the EOS visit for the base study A536-03 prior to C1D1 of A536-05 are considered "patients with treatment interruption." These patients will have a 28-day screening period to allow them to be re-assessed for eligibility by meeting additional inclusion criteria, as defined in protocol Section 9.2.

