#### 5.8.2.2. RBC Transfusion Independence

For patients with  $\geq 2$  units of RBC transfusion at baseline, RBC transfusion independence (RBC-TI) response is defined as not requiring RBC transfusion for 8 or more weeks while on treatment.

The proportion of RBC-TI responders will be estimated by a point estimate along with the exact 95% confidence interval based on binomial distribution. The denominator is the number of patients with  $\geq 2$  units of RBC transfusion at baseline.

Time to RBC-TI will be defined as the time from the first dose date to the starting date of the first consecutive 8-week interval not requiring RBC transfusion. Duration of RBC-TI will be calculated as the longest period of time not requiring RBC transfusion during treatment and will be censored at the analysis cutoff date for ongoing responses.

Both time to and duration of RBC-TI will be analyzed as continuous variables and summarized by descriptive statistics for RBC-TI responders only. Duration of RBC-TI will also be analyzed as a time to event variable using Kaplan-Meier method.

The derivations of RBC-TI response, time to and duration of RBC-TI will be listed for each patient.

RBC-TI responders may experience multiple periods of  $\geq 8$  weeks of RBC-TI response. For all RBC-TI responders, the number of episodes and cumulative duration will be summarized. As an exploratory analysis, the cumulative duration of the multiple responses will be analyzed using Kaplan-Meier method.

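### Kaplan-Meier duration of HI-E and RBC-TI uses each patient's longest episode, which biases the median upward and ties it to follow-up when responses recur; time to first loss is not planned

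*SAP*

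**What the plan says.** SAP section 5.8.2.5 defines duration of HI-E response by transfusion group. For LTB patients, "duration of HI-E response will be calculated as the longest interval during which all hemoglobin measurements" stay at least 1.5 g/dL above baseline. For HTB patients it is the longest run of consecutive rolling 8-week intervals that meet the criterion. The section then adds: "When there are multiple disjoint intervals with response, the longest interval will be used". On censoring: "Patients with response ongoing by the analysis cutoff day will be censored at that date". Beyond descriptive statistics, "duration of HI-E response will also be analyzed as a time to event endpoint".

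SAP section 5.8.2.2 treats transfusion independence in the same way: "Duration of RBC-TI will be calculated as the longest period of time not requiring RBC transfusion during treatment", and "Duration of RBC-TI will also be analyzed as a time to event variable using Kaplan-Meier method".

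Time to response is defined differently. In both sections it runs from the first dose to the start of the first qualifying 8-week interval.

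Both sections recognise that a responder may have several periods of response. They plan a summary of the number of episodes and of cumulative duration, and an exploratory Kaplan-Meier analysis of cumulative duration. Neither plans an analysis of the first episode.

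Duration of HI-E is a named secondary objective (Protocol 8.2, SAP 2). Duration of RBC-TI is not; the objective there is the rate. Protocol 15.2.3 promises a Kaplan-Meier curve, a median and a 95% interval for time-to-event endpoints, but does not say which episode counts.

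**The concern.** A Kaplan-Meier median for duration of response is normally read as the time from gaining a response to losing it. Taking the longest episode answers another question: how long was the best run observed. For a patient who loses a response and later has a longer one, the first loss is not counted as an event.

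Three consequences follow when responses recur:

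- The median is biased upward as an estimate of how long a response lasts once achieved.
- It depends on follow-up. The maximum grows with the time observed, and that time also sets the censoring. On the natural reading of the censoring rule, an ongoing episode is censored only if it is already the longest; otherwise it drops out and an earlier completed episode supplies the event.
- Time to response and duration may come from different episodes, so they cannot be read together as one course of response.

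Recurrence is a realistic prospect here. One hemoglobin value below the 1.5 g/dL increase ends an LTB interval, and one transfusion ends RBC-TI. Protocol 10.8 holds dosing at hemoglobin of 12 g/dL or more and resumes it below 11 g/dL. A responder with baseline 9.5 g/dL has a response threshold of 9.5 + 1.5 = 11.0 g/dL, so once held must fall below that threshold before dosing resumes. Treatment is given "every 3 weeks for up to 87 cycles or up to 1825 days, whichever occurs first", which leaves room for several episodes.

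**Working it through.** **Plan's own figure.** There is none to reproduce. The documents give no expected duration, number of episodes or recurrence rate.

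**Direction.** Let a responder have episodes D1, ..., Dk. Then D1 ≤ max(D1, ..., Dk) ≤ D1 + ... + Dk. The longest and the cumulative durations are both at or above the first-episode duration for every patient, so every duration summary now planned errs the same way.

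**Observation window.** The analysis cutoff day is "defined as the last dose + 56 days or the last date from transfusion record data, whichever is earlier". In A536-05 alone the longest window is (1825 + 56)/7 = about 269 weeks.

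**Size, analytic.** Assume k independent episodes with the same exponential distribution. The ratio of the median of the longest to the median of one is

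r(k) = −ln(1 − 0.5^(1/k)) / ln 2.

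For k = 2: −ln(1 − 0.7071)/0.6931 = 1.77. For k = 3 it is 2.28, and for k = 4 it is 2.65.

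A qualifying response lasts at least 8 weeks, so take an episode as 8 weeks plus an exponential time, with single-episode median M weeks. The ratio becomes [8 + (M − 8) × r(k)]/M. For M = 26 and k = 2: (8 + 18 × 1.77)/26 = 1.53.

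| Episodes per responder | No minimum | M = 16 | M = 26 | M = 52 |
|---|---|---|---|---|
| 2 | 1.77 | 1.39 | 1.53 | 1.65 |
| 3 | 2.28 | 1.64 | 1.88 | 2.08 |
| 4 | 2.65 | 1.83 | 2.14 | 2.40 |

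If only half of responders have a second episode, the median of the longest solves 0.5F + 0.5F² = 0.5, so F = 0.618 and the ratio without a minimum is −ln(1 − 0.618)/ln 2 = 1.39. With the 8-week minimum it is 1.19, 1.27 and 1.33 for M = 16, 26 and 52.

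**Size, simulation with censoring.** Response episodes (8 weeks plus exponential) alternated with exponential gaps, and an episode ongoing at cutoff was censored; 6,000 patients per scenario. Assumed inputs: M = 16, 26, 52 or 104 weeks; mean gap 8 or 26 weeks; probability of a new response after each loss 0.5 or 1; follow-up fixed at 104 or 269 weeks, or exponential with median 60 or 104 weeks, capped at 283. That is 4 × 2 × 2 × 4 = 64 scenarios. Both medians were reached in 60; the other four had M = 104 with 104 weeks of follow-up. A separate run with follow-up uniform over 26 to 260 weeks, mean episode 16 to 52 weeks, gaps of 8 to 16 weeks and 3,000 patients per setting added a recurrence probability of 0.25.

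| Probability of a new response after each loss | Longest/first ratio of Kaplan-Meier medians |
|---|---|
| 0.25 (separate run) | 1.08 to 1.16 |
| 0.5 | 1.16 to 1.50 |
| 1 | 1.36 to 2.59 |

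**Dependence on follow-up.** Take M = 26, mean gap 8 weeks, and recurrence after every loss. Lengthening follow-up from 104 to 269 weeks leaves the first-episode median near its true 26 weeks (25.6 and 26.5) but moves the longest-episode median from 47.0 to 68.6 weeks. With recurrence probability 0.5 the corresponding move is small, from 34.8 to 36.6 weeks.

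**The case against.** The rule is written down in advance and applied mechanically, so it leaves the analyst no discretion. The SAP does not ignore recurrence: it plans episode counts and cumulative duration, and lists complete hemoglobin and transfusion records for each patient. The study's primary objective is safety, all summaries are descriptive, and no test, power figure or decision rule rests on this median.

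Time to first loss has weaknesses of its own. It can reflect a dose hold (Protocol 10.8), a permitted administrative interruption between Cycles 17 and 18 or 35 and 36 (Protocol 10.10), a transfusion given for comorbidity (Protocol 10.2.2), or a single low hemoglobin value. Neither quantity is uniquely correct.

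Most of this stands, and it argues for keeping the longest-episode analysis under a clear label. It does not remove the gap. Counts and cumulative durations give no time to first loss, and in a single-arm descriptive study the reported median is itself the result.

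Two stronger readings are tempting. A reader might infer that the rule roughly doubles the median. The documents do not support that, because they say nothing on how often responses recur; a ratio near 2 needs roughly three or more comparable episodes in most responders. A reader might also infer that the plan hides the loss of a first response. It does not: the extra episodes appear in the planned counts, and a patient whose longest episode ends still has an event.

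**Conclusion.** The point holds as a matter of what is estimated. As an estimate of how long a response lasts once achieved, the planned median is biased upward whenever responses recur, and it shifts with length of follow-up. The direction is certain. The size is not: about 1.1 to 1.5 times the first-episode median if half or fewer of losses are followed by a new response, and about 1.4 to 2.6 times if every loss is. If no responder has a second episode, the two medians coincide.

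These ranges rest on assumed episode lengths, gaps and follow-up, and on independent episodes within a patient; correlation within patients would lower the ratio. The 8-week minimum comes from the responder definition, since the LTB duration rule does not restate it.

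The consequence is a reported figure for a named secondary objective that is open to misreading. The safety objective and the response rates are unaffected.

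**What to change.** In SAP sections 5.8.2.5 and 5.8.2.2, add a Kaplan-Meier analysis from the start of the first responding interval to first loss of response, censored at the analysis cutoff day if no loss has occurred. Define loss using the criteria already in the plan:

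- **LTB:** the first evaluable hemoglobin below the 1.5 g/dL increase.
- **HTB:** the end of the first run of qualifying 8-week intervals.
- **RBC-TI:** the first transfusion after the period starts.

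SAP section 5.8.2.3 has two LTB versions of HI-E (all values, or mean value), so state which one starts the clock. The present duration rule uses all values.

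Report this beside the existing analysis, label the latter as longest episode in tables and text, and keep the episode counts and cumulative summaries. Time to response and first-episode duration will then describe the same episode.

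The cost is one extra derived variable per endpoint, from data already collected, and a less favourable reported median if responses recur. Because first loss can also reflect dose holds or incidental transfusions, both analyses should be kept.
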